1.3.3. Early Termination and Follow-up

If study intervention is permanently discontinued, the participant will be asked to remain in the study after the Follow-up visit without study intervention and continue to comply with study visit schedules for approximately 2 years or until study end, whichever occurs first. Refer to Section 4.1 for further details.

Procedure	ET	28-Day Follow-up	6-Month Follow-up	Notes
Visit Identifier	NA	18	19	
Day	NA	EOS 28 days after last dose	182 days after discontinuation for neurological or auditory adverse event	
Visit Window (±Days)	+7	±7	±30	ET visit will be performed on the last day the participant takes the study intervention or as soon as possible thereafter. Follow-up visit is 28 days after last dose. 6-Month Follow-up visit occurs 6 months after the last dose of study intervention for any participant who discontinues the study due to a neurological or auditory adverse event (See Section 10.7).
Medical Procedures				
Full physical examination, including dermatological full body examination	X			See Section 8.2.1 .
Targeted physical examination		X	X	See Section 8.2.1 .
Neurological examination by a neurologist	X		X (see Note)	See Section 10.7.2 for follow-up assessment of participants who discontinue due to a neurological adverse event. Neurological examination will include the Neuropathy Assessment. Refer to the Manuals for General Neurological and Neuropathy Assessments for more information. See Section 8.2.5 . Neurological examination not collected during ET visit for participants who have completed the Month 15E visit, unless these assessments are relevant to the reason for discontinuation. If neurological examination required, the same neurologist who saw the participant for the first 24 months should also do the consultation when possible.
Vital Signs	X	X	X	See Section 8.2.2 .

Procedure	ET	28-Day Follow-up	6-Month Follow-up	Notes
Visit Identifier	NA	18	19	
Day	NA	EOS 28 days after last dose	182 days after discontinuation for neurological or auditory adverse event	
Visit Window (±Days)	+7	±7	±30	ET visit will be performed on the last day the participant takes the study intervention or as soon as possible thereafter. Follow-up visit is 28 days after last dose. 6-Month Follow-up visit occurs 6 months after the last dose of study intervention for any participant who discontinues the study due to a neurological or auditory adverse event (See Section 10.7).

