4.4. End of Study Definition

A participant is considered to have completed the study:

- If participant has completed all phases of TP1 & TP2, including follow-up visit and does not continue to TP3 due to local commercial availability of PF-06651600 for AA; OR
- If participant has completed all phases of TP3, including Follow-up Visit; OR
- If participant discontinued from the study during TP3 due to local commercial availability of PF 06651600 for AA.

The end of the study is defined as the date of the last visit of the last participant in the study.

The primary completion date (PCD) is defined as the date when the last participant completes the Month 9 Visit of the Placebo-Controlled Phase.

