5.1. Inclusion Criteria

Participants are eligible to be included in the study only if all of the following criteria apply:

Type of Participant and Disease Characteristics

1. Participants must meet the following AA criteria:

- Have a clinical diagnosis of AA. Other etiologies of hair loss coexistent with AA are allowed.
- $\geq 25\%$ scalp hair loss due to AA (including AT and AU) measured by SALT at screening which, in the opinion of the investigator, is appropriate for systemic therapy.
- Hair loss must be carefully reviewed to verify that $\geq 25\%$ terminal scalp hair loss is due to AA (ie, SALT [AA] score is ≥ 25). If in cases of concomitant AA and other etiologies of alopecia, it cannot be verified that SALT (AA) score is ≥ 25 , then the participant must be excluded from the study.

Hearing and Neurological Assessments at Screening

2. Participants must have normal hearing and BAEP assessed by the audiology professional and confirmed by the central reader.
3. Participants must have a normal neurological examination by a neurologist and absence of peripheral neuropathy by history, symptoms, and the neuropathy assessment. Participants with stable unilateral carpal tunnel syndrome or stable unilateral ulnar entrapment on neurological examination or history are allowed in the study.

Age

4. All participants must be 18 to 50 years of age at the time they sign the informed consent.

Sex

5. Male or Female

Contraceptive use by men or women should be consistent with local regulations regarding the methods of contraception for those participating in clinical studies.

The study protocol requirements regarding contraception are as follows:

- a. Male participants:
No contraceptive measures required.
- b. Female participants:
 - A female participant is eligible to participate if she is not pregnant or breastfeeding, and at least one of the following conditions applies:
 - Is not a woman of childbearing potential (WOCBP), See Section 10.4.

OR

- Is a WOCBP and using a contraceptive method that is highly effective, with a failure rate of <1%, as described in Section 10.4 during the intervention period and for at least 28 days after the last dose of study intervention. The investigator should evaluate the effectiveness of the contraceptive method in relationship to the first dose of study intervention.

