5.3. Lifestyle Considerations

5.3.1. Contraception

Participants who are WOCBP must agree to use one highly effective method of contraception (as specified in Section 10.4), as applicable.

The investigator or his/her designee, in consultation with the participant, will confirm that the participant has selected an appropriate method of contraception for the individual participant from the permitted list of contraception methods (See Section 10.4), and will confirm that the participant has been instructed in its consistent and correct use. At time points indicated in the SoA (Section 1.3), the investigator or designee will inform the participant of the need to use highly effective contraception consistently and correctly and document the conversation and the participant's affirmation in the participant's chart (participants need to affirm their consistent and correct use of at least 1 of the selected methods of contraception). In addition, the investigator or designee will instruct the participant to call immediately if the selected contraception method is discontinued and document the requirement to use an alternate protocol-specified method, including if the participant will no longer use abstinence as the selected contraception method or if pregnancy is known or suspected in the participant or partner. The contraception check for WOCBP will be performed during each study visit and monthly between study visits at the time of the phone contact to check the at-home pregnancy test results (see Section 8.2.13).

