7. DISCONTINUATION OF STUDY INTERVENTION AND PARTICIPANT DISCONTINUATION/WITHDRAWAL

7.1. Discontinuation of Study Intervention

7.1.1. Permanent discontinuation

In rare instances, it may be necessary for a participant to permanently discontinue study intervention (ie, definitive discontinuation). Reasons for definitive discontinuation of study intervention include the following: treatment-related SAEs, serious infections, and other events as described in [Section 10.7.2](#).

Note that discontinuation of study intervention does not represent withdrawal from the study. If study intervention is definitively discontinued, the participant will remain in the study to be evaluated for the assessments at the Early Termination (ET) and Follow-up visits (per the SoA [Section 1.3]). See the SoA (Section 1.3) for data to be collected at the time of discontinuation of study intervention and follow-up and for any further evaluations that need to be completed.

In the event of discontinuation of study intervention, it must be documented on the appropriate CRF/in the medical records whether the participant is discontinuing further receipt of study intervention or also from study procedures, posttreatment study follow-up, and/or future collection of additional information.

Refer to Section 10.7 for discontinuation criteria.

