7.1.1.1. Observation Period

Participants will be asked to remain in the study after the Follow-up visit without study intervention. The Period during which participants are in the study after having permanently discontinued study intervention is referred to as the Observation Period. During this period participants will continue to comply with study visit schedules for approximately 2 years or until study end, whichever occurs first. At visits during the Observation Period, only the SALT, PGI-C, and concomitant medications/treatments will be collected at the visits specified in the applicable SoAs in Section 1.3.2; AE and SAE reporting will follow the guidelines in Section 8.3.

Participants will complete the final visit in the Observation Period approximately 2 years after the last dose of study intervention or at study end whichever occurs first as follows:

- at the protocol-scheduled visit 24 months after the last dose of study intervention, OR
- at the next scheduled visit after the 24-month time point (if no scheduled visit falls at the 24-month time point), OR
- at study end.

For example, if the last dose of study intervention occurs around the time of Month 22E then the final visit in the Observation Period would be conducted at Month 51E (ie, the next closest scheduled visit occurring 24 months after Month 22).

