8.3.1. Time Period and Frequency for Collecting AE and SAE Information

The time period for actively eliciting and collecting AEs and SAEs (“active collection period”) for each participant begins from the time the participant provides informed consent, which is obtained before the participant’s participation in the study (ie, before undergoing any study-related procedure and/or receiving study intervention), through and including a minimum of 28 calendar days, except as indicated below, after the last administration of the study intervention.

The time period for actively eliciting and collecting AEs and SAEs (“active collection period”) for each participant begins from the time the participant provides informed consent, which is obtained before the participant’s participation in the study (ie, before undergoing any study-related procedure and/or receiving study intervention), through and including Visit 19.

Follow up by the investigator continues throughout and after the active collection period and until the AE or SAE or its sequelae resolve or stabilize at a level acceptable to the investigator, and Pfizer concurs with that assessment.

For participants who are screen failures, the active collection period ends when screen failure status is determined.

If the participant withdraws from the study and also withdraws consent for the collection of future information, the active collection period ends when consent is withdrawn.

If a participant definitively discontinues or temporarily discontinues study intervention because of an AE or SAE, the AE or SAE must be recorded on the CRF and the SAE reported using the CT SAE Report Form.

Investigators are not obligated to actively seek AEs or SAEs after the participant has concluded study participation. However, if the investigator learns of any SAE, including a death, at any time after a participant has completed the study, and he/she considers the event to be reasonably related to the study intervention, the investigator must promptly report the SAE to Pfizer using the CT SAE Report Form.

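### The ±7-day window lets the final follow-up visit fall up to 7 days before the 28-day minimum for adverse event collection, and completers have no later scheduled contact

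*Protocol*

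**What the plan says.** **Timing of the last visit.** The Early Termination and Follow-up schedule (Protocol 1.3.3) places Visit 18, labelled EOS, at Day 28 ("Follow-up visit is 28 days after last dose") and allows ±7 days.

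**Length of adverse event collection.** Protocol 8.3.1 has active AE and SAE collection run from consent "through and including a minimum of 28 calendar days, except as indicated below, after the last administration of the study intervention". The next paragraph of the same section gives a different end, "through and including Visit 19". It adds later that investigators have no duty to look actively for events once a participant's participation has ended.

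**Contacts after Visit 18.**
- Visit 19, the 6-month follow-up, is scheduled in 1.3.3 only for participants who discontinue because of a neurological or auditory adverse event.
- The Observation Period (7.1.1.1) provides later visits: "Participants will be asked to remain in the study after the Follow-up visit without study intervention". It is defined for those who have permanently stopped study intervention, which 7.1.1 presents as uncommon: "In rare instances, it may be necessary for a participant to permanently discontinue study intervention".
- For completers, 4.4 ends participation with the Follow-up Visit, for example "If participant has completed all phases of TP3, including Follow-up Visit".
- Phone contacts between visits exist only for women of childbearing potential, "at the time of the phone contact to check the at-home pregnancy test results" (5.3.1). Under 8.2.13 the home tests end at Month 51E/EOT.

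**Analysis.** SAP 3.6.1 caps the post-treatment AE risk period at last dose plus 35 days or at last contact, whichever is earlier.

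**The concern.** The visit that is meant to close out safety follow-up may be held before the period it closes out has ended. For a completer, or for someone who stops, declines the Observation Period and has no Visit 19, Visit 18 is the last scheduled contact. If it takes place on Day 21, no planned enquiry covers Days 22 to 28. The duty in 8.3.1 still runs to Day 28, but nothing in the schedule carries it out. The sentence on not seeking events after participation ends could lead a site to treat the duty as finished once the end-of-study visit is done.

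This is a safety study, with the incidence of treatment-emergent and serious events among its secondary endpoints. What is at stake is whether the protocol's minimum post-treatment follow-up is met in every participant without relying on an unplanned call. A lesser point is pregnancy: contraception must continue "during the intervention period and for at least 28 days after the last dose of study intervention" (5.1), and the last scheduled pregnancy test, at Visit 18, can fall before that period ends. No testing rule is broken by this.

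**Working it through.** **Inputs**
- Visit 18 target: Day 28 after last dose; window ±7 days (Protocol 1.3.3).
- Minimum active AE/SAE collection: 28 calendar days after last dose (Protocol 8.3.1).
- Month 15E = Day 451E, Month 21E = Day 631E, Month 51E = Day 1531E (Protocol 1.3.2).
- Risk-period cap: last dose + 35 days (SAP 3.6.1).

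**Step 1: does ±7 permit early visits?** Protocol Table 4 prints the day ranges for the schedule's windows. 91 ± 7 gives Days 84 to 98, 451 ± 7 gives Days 444 to 458, and 1531 ± 7 gives Days 1524 to 1538. All three match the table, so ±7 is two-sided in this protocol.

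**Step 2: permitted days for Visit 18.** 28 - 7 = Day 21; 28 + 7 = Day 35. That is 35 - 21 + 1 = 15 permitted days, of which Days 21 to 27 (7 days) fall before the minimum. This is 7 of 15 permitted days, not a share of participants.

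**Step 3: largest shortfall.** 28 - 21 = 7 days; 7/28 = 25% of the required period.

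**Step 4: is there a later scheduled contact?**

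| Participant | Scheduled contact after Visit 18 |
|---|---|
| Completes TP2 and does not enter TP3 | None |
| Completes TP3 | None |
| Stops early and enters the Observation Period | Observation visits |
| Stops early for a neurological or auditory event | Visit 19 |
| Stops early for another reason and declines the Observation Period | None |

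**Step 5: size against TP3 follow-up.**
- Full TP3: 1531 - 451 = 1,080 days of planned dosing; 7/(1,080 + 28) = 0.6%.
- TP3 ending at Month 21E: 631 - 451 = 180 days; 7/(180 + 28) = 3.4%.

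**Step 6: effect through the SAP risk period.** Only the TP3 definitions use the date of the last visit. There, last contact is the later of study discontinuation and last visit. If both are Day 21, the risk period ends 35 - 21 = 14 days before its cap. The documents do not say how the discontinuation date is set for a completer, so this truncation is possible but not certain. SAP 8.3 reports TP3 as a single group.

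**Step 7: the proposed window.** -0/+7 gives Days 28 to 35, which is 8 permitted days. The shortfall is 0 days, and the latest day coincides with the SAP cap.

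**The case against.** The strongest reply is that no rule is contradicted. The 28-day duty in 8.3.1 is not tied to Visit 18, so a site that holds the visit on Day 21 must still collect events to Day 28, and the protocol allows unscheduled visits. The target is already Day 28, and harm arises only if a site uses the early half of the window and then omits the required contact. Much of the early-stopping population is covered elsewhere: 10.7.2 asks for follow-up visits until relevant events resolve or are stable, permanent discontinuers are asked to stay on for observation, and related SAEs learned of later must still be reported. No hypothesis is tested, so no decision can change.

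Most of this stands and limits the size of the point. It does not remove the mismatch. A site can comply with every scheduled visit and miss the minimum, and 8.3.1 gives it some reason to think it has finished once the end-of-study visit is done.

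It can also be said that the two end points in 8.3.1 are the clearer defect. They do need reconciling for participants who have no Visit 19, but rewording that section alone would still leave completers without a contact on or after Day 28.

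**Conclusion.** The concern holds. A compliant Visit 18 can fall as early as Day 21, up to 7 days short of the 28-day minimum, and no scheduled contact follows for completers or for those who stop, decline observation and have no Visit 19.

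The consequence is modest. At most 7 days of planned AE enquiry are missing per affected participant. The number affected could be anywhere from none to everyone whose last contact is Visit 18, since no distribution of visit days is given. The primary BAEP estimate is unaffected. No between-arm contrast depends on the last visit date, because only the single-group TP3 risk period uses it.

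The conclusion assumes that ±7 carries the same two-sided meaning for Visit 18 as in Table 4, and that sites make no unscheduled contact after an early Visit 18. The change is worth making because the gap concerns safety follow-up in a safety study and costs almost nothing to close.

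**What to change.** In Protocol 1.3.3, change the Visit 18 window from ±7 to -0/+7 days (Days 28 to 35 after last dose). A one-sided window already appears in the same row for the Early Termination visit.

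The cost is one table entry and no added visit. Permitted days fall from 15 to 8, a loss of 7, and visits on Days 21 to 27 would become deviations.

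If the early half of the window must be kept, add a note requiring an AE telephone contact on Days 28 to 35 whenever Visit 18 is held before Day 28. Sites already make phone contacts for home pregnancy tests, but this option adds a contact that the window change avoids.

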2. INTRODUCTION

2.1. Study Rationale

PF-06651600 is being developed as an oral treatment for patients with alopecia areata (AA) based on its mechanism of action and the clinical results obtained in Phase 1 and Phase 2 studies. This study is specifically designed to evaluate the safety of PF-06651600 in adult participants with AA. This includes assessments of brainstem auditory evoked potentials (BAEPs) and intraepidermal nerve fiber (IENF) histology. The BAEP and IENF assessments are being performed to investigate the clinical relevance of changes observed in non-clinical toxicity studies in dogs treated with PF-06651600 (see Section 4.2).

2.2. Background

AA is a chronic, relapsing, T-cell mediated autoimmune disorder characterized by non-scarring hair loss affecting children and adults across all ages, races, and sexes.^(1,2) AA is associated with other immune diseases including asthma, allergic rhinitis, atopic dermatitis, and autoimmune diseases such as thyroiditis and vitiligo.⁽²⁾

Clinical presentation of AA can be limited to small, circular patches of scalp hair loss (patchy hair loss, alopecia focalis), involve complete loss of hair on the scalp (alopecia totalis [AT]), or total loss of hair on the scalp and body (alopecia universalis [AU]).⁽³⁾ Patchy alopecia is the most common form of AA which may develop into the more extensive and often treatment-resistant forms of AA, especially with earlier age of onset.⁽⁴⁾ It is estimated that AA affects as many as 6 to 7 million individuals in the United States (US)⁽²⁾ and 147 million worldwide.⁽⁵⁾

Depression, anxiety, and panic disorders are often observed in patients with AA and the coping mechanisms of AA patients mirror those of grief and bereavement.^(6,7) A substantial body of evidence demonstrates a widespread impact of AA on the psychological health of both adult and pediatric patients with AA, including impairment in self-esteem, increased incidence of anxiety and depressive disorders and other psychological conditions,⁽⁸⁻¹²⁾ problems with social relations,⁽¹³⁾ decreased health-related quality of life (HRQoL) and general quality of life (QoL), as well as the QoL of their families.^(5, 14-21)

No drugs have been approved for the treatment of AA in most countries/regions, including the US and the European Union (EU). Review of the treatment guidelines and recommendations indicate that a number of off-label therapies are frequently used after assessing factors such as the age of the patient, disease extent, and disease duration. There is neither a cure for AA nor is there a therapy convincingly demonstrated to induce and sustain remission long term.⁽²²⁻²⁶⁾

CD8+ T cells, natural killer (NK) cells, and mast cells are involved in the pathogenesis of AA. The possible inflammatory pathways in AA include cytokines from the type 1 helper T cell (TH1) axis, including interferon (IFN) alpha (α), IFN gamma (γ), and IFN γ -induced protein 10 (IP-10).^(27,28) Mouse models have shown that interleukin (IL)-2 and IL-15 play a

role in the initiation of auto-reactive CD8⁺ cells that attack hair follicles. IL-12 and IL-23 may also play a role in the pathogenesis of AA.⁽²⁹⁾

The cytokine signaling pathways of IFN γ and IL-15, among others, can be blocked via Janus kinase (JAK) inhibition, supporting the rationale of a JAK inhibitor in the treatment of AA.⁽³⁰⁾ Indeed, treatment with the JAK inhibitors tofacitinib and ruxolitinib is reported to reverse AA in a mouse model.⁽³¹⁾ Clinically, there are case reports and case series reporting that these JAK inhibitors demonstrate efficacy in AA.⁽³¹⁻³⁹⁾

The tyrosine kinase expressed in hepatocellular carcinoma (TEC) kinase family of protein kinases consists of five members (Bruton's tyrosine kinase [BTK], bone marrow tyrosine kinase on chromosome X [BMX], interleukin (IL)-2 inducible T cell kinase [ITK], TEC and tyrosine kinase expressed in T cells [TXK]), primarily expressed in hematopoietic cells.^(40, 41) T cells express three TEC kinases, ITK, TEC and TXK that are activated downstream of the T cell receptor (TCR). BTK plays crucial roles in B cell development and function and is activated downstream of the B cell receptor (BCR). Additionally, TEC kinases have overlapping roles in mediating activation signals in NK cells, mast cells and other hematopoietic cells.⁽⁴²⁾ Since CD8⁺ T cells, NK cells, and mast cells have all been implicated in the pathophysiology of AA,^(28, 31, 43, 44) inhibition of TEC kinases has the potential to contribute to efficacy in this disease by modulating the functional activity of these pathogenic effector cells.

PF-06651600 is a covalent and irreversible inhibitor of Janus kinase 3 (JAK3) with high selectivity over the other three JAK isoforms (JAK1, JAK2, and tyrosine kinase 2 [TYK2]). PF-06651600 also inhibits irreversibly the TEC family kinases with selectivity over the broader human kinome. Treatment with PF-06651600 is expected to inhibit the inflammatory pathways mediated by IL-7, IL-15, and IL-21, all implicated in AA. Moreover, due to lack of activity against the other JAK isoforms, PF-06651600 is expected to spare immunoregulatory cytokines such as IL-10, IL-27 and IL-35, which are critical to the maintenance of immunosuppressive functions and immune homeostasis.

